8.3. Secondary endpoints

Related to secondary objective 1:

- 1- Genetic kidney- and immune-related risk factors measured as number of variants in kidney- and immune-related genes, associated to INS incidence, progression, and poor response to therapy.
- 2- A methylation profile of target genes measured as number of hypomethylated and hypermethylated immune-related gene regions, related to a faster progression to kidney failure and altered immune profile.

Related to secondary objective 2:

- 3- Difference in terms of % and absolute number of subpopulations of B cells and T cells among patients classified as SRNS/SDNS, IRNS, and healthy children.
- 4- Changes in immune cell subsets genes, expressed as the number of expressed genes per cell (log-transformed Unique Molecular Identifier counts, UMI), among patients classified as SRNS/SDNS, IRNS, and healthy children.
- 5- Signaling dynamics changes, measured as number of phosphosites for each target protein expressed in the subpopulation of primary B and T cells, implicated in the development of kidney damage in INS.

Related to secondary objective 3:

- 6- Difference in the urine EV concentration expressed as total number/urine creatinine levels, and size as mean diameter, among patients classified as SRNS/SDNS, IRNS, and healthy children.
- 7- Difference in the urine and serum EV surface proteome phenotype, in terms of the ratio of the average of label-free quantification intensities for each detected EV protein, among patients classified as SRNS/SDNS, IRNS, and healthy children.

Dipartimento Area Materno - Infatile

SC NEFROLOGIA E DIALISI PEDIATRICA – TRAPIANTI DI RENE – Direttore: [name]

[contact]

email: [contact]

8- Difference in the serum proteome, in terms of the ratio of average of label-free quantification intensities for each detected protein, among patients classified as SRNS/SDNS, IRNS, and healthy children.

Related to secondary objective 4:

9- To describe different molecular signatures (characteristics) for healthy children group in the same way done for the primary endpoint.

9. Enrollment and inclusion/exclusion criteria

The recruiting centers that will be involved in the study are listed in Appendix 1.

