10.9 Sample collection for molecular analysis

The following samples are needed:

1. Blood sampling: for INS patients and controls, two additional aliquots of blood (a maximum of 10-12 mL at a single time; body weight >12 kg) based on the patient's age and clinical condition during the sampling will be collected in the occasion of routine laboratory tests.
2. Urine sampling: spot urines (20-30 mL) from residual urine from routine laboratory tests.

Detailed sample processing:

- **Whole blood.** Blood collection for genetic and epigenetic will be performed for all NS patients recruited into the study. Whole blood will be collected and stored at 4°C for analysis. Shipment of samples will be done at 4°C.
- **Mononuclear cells from peripheral blood.** Whole blood will be isolated using the BD Vacutainer® CPT™ Mononuclear Cell Preparation Tube. Peripheral blood mononuclear cells (PBMCs) will be isolated by Ficoll procedure followed by washing step with PBS, and freezed in Cell Storage Media at density of 10^6 cells/vial and stored in liquid nitrogen or -80°C. Shipment of samples will be done by dry ice.
- **Urine.** Urine samples will be centrifuged at 3,000 g for 15 minutes to remove large membrane fragments and other debris. A protease inhibitor cocktail will be added immediately (PI inhibitor). Urine aliquots will be stored at -80°C. Shipment of samples will be done by dry ice.
- **Serum.** The serum will be obtained by direct cascade activation of coagulation from whole blood. The blood will then be centrifuged at 3,000g for 20 minutes to remove corpuscular components along with clots and debris. Serum aliquots will be stored at -80°C. Shipment of samples will be done by dry ice.

Urine and serum will be centralised at Heidelberg University Hospital. The storage of peripheral blood mononuclear cells (PBMCs) will be centralized at the coordinating centre.

Any residues of biological material that will not be used for the study will be eliminated at the end

Dipartimento Area Materno - Infatile

SC NEFROLOGIA E DIALISI PEDIATRICA – TRAPIANTI DI RENE – Direttore: [name]

[contact]

email: [contact]

of the study.

11. Detailed technical methodologies

Exome sequencing (collaborator involved: Medical University Gdansk). DNA samples extracted from blood leukocytes will be subject to sequencing using TruSeqExome Enrichment Kits according to the manufacturer's instructions (Illumina). Data analysis will be carried out as previously described (11).

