EV isolation and characterization (collaborator involved: the University of Milano). Purification of EVs will be obtained by size exclusion chromatography using 70 nm qEV columns (IZON) after a 100 kDa centrifugal filter (Sartorius). The concentration and size distribution of EVs will be measured using NanoSight LS300 (NanoSight Ltd). EVs integrity will be characterized by transmission Electron microscopy (TEM) by adherence to glow-discharged formvar-coated copper grids 300 mesh.

Single vesicles studies (collaborator involved: the University of Milano). EV evaluation at single levels will be performed following the pipeline described by (12). Super-resolution microscopy will be performed using the Nanoimager S Mark II microscope from ONI (Oxford Nanoimaging, Oxford, UK) equipped with a 100X. Tetraspanins and selective markers will be tested using the Apex Antibody Labelling Kit (Invitrogen) according to the manufacturer's protocol. Samples will be also analyzed with ExoView Plasma Tetraspanin kit on an ExoView R100 instrument (NanoView Biosciences) following the manufacturer's instructions.

EV protein corona and lipid evaluation (collaborator involved: the University of Milano). EVs surface phenotype will be analyzed using the MACSplex kit (Miltenyi Biotec) on a BD FACSCanto II (Becton Dickinson) as (12). Proteomic studies will be then performed by two-dimensional difference gel electrophoresis (2D-DIGE) followed by liquid chromatography-tandem mass spectrometry (LC-MS) as (13). Surface proteins will be separated from the ones from the lumen. Lipidomic profile will be also evaluated by gas chromatography (GC)-MS.

Proteomics and phospho-proteomics (collaborator involved: Cologne University Hospital). For expression profiling and characterization of cellular phosphor-proteomes, a fully established standard pipeline at the Cellular Stress Responses in Aging-Associated Diseases and the Centre for Molecular Medicine Cologne will be used. Proteins are purified, alkylated, and digested. Peptides are purified after acidification by a Stage-Tip protocol using an SDB-RPS-Matrix (Styrene Divinyl Benzene reverse phase sulfonate-Matrix and measured in a Q Exactive Plus Tandem or a LTQ Orbitrap XL spectrometer. Raw data is processed using the MaxQuant software, is compared to reference datasets, and is analyzed and displayed using Perseus software. To obtain insights into the

Dipartimento Area Materno - Infatile

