SC NEFROLOGIA E DIALISI PEDIATRICA – TRAPIANTI DI RENE – Direttore: [name]

[contact]

email: [contact]

activation of specific signaling cascades by posttranslational modification (phosphorylation) we will also characterize the phospho-proteome. Phosphorylated peptides are enriched after standard isolation and purification with a special kit (High-Select Fe-NTA Phospho-peptide Enrichment Kit). For an unbiased serum proteomics approach, we can rely on the established fully automated clinical pipeline using liquid handling robots and state-of-the-art mass spectrometry platforms, including the latest generation Orbitrap Exploris 480. The approach enables the detection and quantification of on average 300 plasma/serum proteins per hour using a data-independent acquisition approach from a 5 µl sample volume.

12. Source Documents

Medical history and all clinical data collected during the study will be collected from each visit's medical records.

Local laboratory records will be used to collect laboratory analysis results.

13. Sample Size

As this is a descriptive and explorative study without inference in the primary endpoint, and given the incidence of childhood idiopathic nephrotic syndrome, which is considered a rare disease, the number of recruiting centers, we foresee enrolling in this study 110 treatment-naïve INS children. A homogeneous age control group of healthy children undergoing minor urological surgical corrections will be enrolled as a control group (n=40 children in 3 years). These numbers are the maximum we can recruit, but at the same time, we think that this study could serve as an important basis for appropriate studies in the future.

14. Data Management

A consortium was created under the direction of the Lead Unit (IRCCS Ca Granda of Milano, [name], Proposal Coordinator) with the Partners involved in the study. At the enrollment visit, a unique code will be assigned to each participant. The de-identification of the data will take place in such a way that people who access the database will not be able to trace the identity of the subjects in any way. Only local investigators will be able to trace the identity of the enrolled subjects.

The data necessary for the study will be recorded in a specific eCRF in a Data Management System validated according to national legislation, provided by the Scientific Management of the Foundation. The platform used will be RedCap (Research Electronic Data Capture).

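### Secondary endpoint 5 counts detected phosphosites, which cannot show a change at sites already detected and elsewhere cannot separate biology from input or instrument depth

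*Protocol*

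**What the plan says.** Section 8.3 sets the measurement variable of endpoint 5: "Signaling dynamics changes, measured as number of phosphosites for each target protein expressed in the subpopulation of primary B and T cells". The endpoint links these changes to the development of kidney damage in INS but names no groups to compare.

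Section 11 (proteomics and phospho-proteomics) states the purpose as insight into "activation of specific signaling cascades by posttranslational modification (phosphorylation) we will also characterize the phospho-proteome". On method it says "Phosphorylated peptides are enriched after standard isolation and purification with a special kit", and samples are "measured in a Q Exactive Plus Tandem or a LTQ Orbitrap XL spectrometer". Data go through MaxQuant and then Perseus. The paragraph states no input amount for the phospho-proteome and no rule that one spectrometer is used throughout.

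Section 10.9 sets the blood for molecular analysis at "a maximum of 10-12 mL at a single time", depending on the child's "age and clinical condition during the sampling". It also says that PBMCs are frozen at 10^6 cells per vial.

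Endpoint 8, by contrast, uses the ratio of average "label-free quantification intensities for each detected protein", and endpoint 7 uses the same kind of measure for vesicle proteins. Both name SRNS/SDNS, IRNS and healthy children as the groups.

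**The concern.** Cascade activation is a change in the amount phosphorylated at given sites. The endpoint records only how many sites per protein were detected. The mismatch has two consequences.

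- **Insensitivity.** If the same sites are detected in two children and one child has much higher phosphorylation at them, the counts are equal.
- **Ambiguity.** Near the detection limit, more cells or a more sensitive instrument raises the count in the same way as more phosphorylation.

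Section 15.2 applies t-tests, Mann-Whitney tests or ANOVA at 0.05 to the secondary endpoints. A technical difference between groups could therefore be reported as a signalling difference, and real activation could be missed. Because the protocol itself fixes the variable, an analysis plan that used intensities would depart from the endpoint as written.

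**Working it through.** The protocol gives no power, effect size or variance for endpoint 5, so there is no figure of its own to reproduce. The check has three parts.

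**1. Metric against purpose**

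| Item | Where | What it measures |
|---|---|---|
| Aim of the assay | Section 11 | activation through phosphorylation (a level) |
| Endpoint 5 | Section 8.3 | number of sites (a detection count) |
| Endpoints 7 and 8 | Section 8.3 | ratio of average intensities (a level) |

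Endpoint 5 is the only one of these mass-spectrometry endpoints that does not use a level.

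**2. Effect of input on the count**

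Assumptions, none from the protocol: log10 site intensity is normal with SD s, a share p of sites lies above the detection limit, and doubling the input raises every intensity by log10(2) = 0.301.

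New share detected = Phi(Phi^-1(p) + 0.301/s). Relative rise in the count = new share / p - 1.

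| p | s | 0.301/s | New share | Rise in count |
|---|---|---|---|---|
| 0.50 | 0.5 | 0.602 | 0.726 | 45% |
| 0.50 | 0.8 | 0.376 | 0.647 | 29% |
| 0.50 | 1.2 | 0.251 | 0.599 | 20% |
| 0.90 | 0.5 | 0.602 | 0.970 | 8% |
| 0.90 | 0.8 | 0.376 | 0.951 | 6% |
| 0.90 | 1.2 | 0.251 | 0.937 | 4% |

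The rise is 4% to 45% with no biological change. It is smallest where most sites are already detected, and that is also where the count is least able to show a real change.

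**3. Simulation of both consequences**

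Assumptions, again not from the protocol: 10 true sites per protein, log2 site abundance normal with mean 0 and SD 2, measurement SD 0.5, and a site counted when it exceeds a limit.

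| Detection limit (log2) | Baseline | Phosphorylation doubled | Input or depth doubled, no biology | Half the sites doubled, half halved |
|---|---|---|---|---|
| -8 | 10.0 | 10.0 | 10.0 | 10.0 |
| -1 | 6.84 | 8.32 | 8.34 | 6.66 |
| 0 | 4.96 | 6.83 | 6.82 | 4.96 |

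With all sites detected (limit -8), a true doubling does not move the count. At limits -1 and 0, a true doubling and a doubling of input give practically the same count. Mixed up- and down-regulation almost cancels.

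Group comparison: 110 patients against 40 controls (numbers from Section 13), two-sided t-test at 0.05, between-sample input SD 0.5 log2, 2,000 runs.

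- Limit -1, no biological difference, equal depth: 4.7% rejections.
- Limit -1, no biological difference, depth 1.41-fold higher in one group: 96.7%.
- Limit -1, no biological difference, depth 2-fold higher in one group: 99.9%.
- Limit -8, true doubling of phosphorylation, equal depth: 0.2%.

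The 4.7% shows that technical variation balanced across the groups does not inflate error. The problem needs a systematic difference between them.

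**The case against.** Several stronger readings are tempting, and the protocol does not support them.

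- **The count misses every change in phosphorylation.** This holds only for sites detected in both states. At limit -1 above, a true doubling moves the count from 6.84 to 8.32. What stands is that such a movement cannot be told from a change in depth.
- **Group differences will follow cell yield.** Endpoint 3 asks whether B- and T-cell subsets differ between groups; it does not say that they do. Freezing at 10^6 cells per vial means that a smaller draw may give fewer vials rather than less material per run. However, it fixes total PBMCs per vial, not the B or T cells recovered, and input per phospho-run is not stated. Confounding is possible, not shown.
- **The site intensities will be thrown away.** Nothing says so. MaxQuant and Perseus processing is planned, and Section 15.1 selects features across all omics. The endpoint simply does not use the intensities.
- **Each sample is an unstimulated snapshot, so dynamics is the wrong word.** Section 11 does not say whether these cells are stimulated. Schedule A plans mononuclear-cell samples at onset, 6 weeks (a footnote may limit this visit to children not in remission at week 4), 12 months and first relapse, so dynamics can mean change over visits.

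It is also fair to say that this is one of nine secondary endpoints in a study described as exploratory, that loading amounts are usually laboratory-procedure detail, and that endpoints 1 and 2 name no groups either. These points limit the weight of the concern. They do not make a count into a measure of activation.

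**Conclusion.** The concern stands in this limited form. As written, endpoint 5 cannot register a change at sites detected in both states, and at other sites it cannot separate biology from input or depth. It does not match the aim in Section 11 and is out of line with endpoints 7 and 8.

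The 4% to 45% rise and the simulated rejection rates are illustrations that rest on assumed distributions and detection limits. Their size would change with other assumptions; their direction would not. The choice of two spectrometers and the variable blood volume make the risk relevant here without proving it. The consequence is confined to the interpretation of one exploratory secondary endpoint. The primary endpoint and the sample size do not depend on it.

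**What to change.** Redefine endpoint 5 as the log2 label-free intensity of each phosphosite, adjusted for the abundance of its parent protein where that is quantified. Compare SRNS/SDNS, IRNS and healthy children at enrolment, and compare within patients over the scheduled mononuclear-cell visits where samples exist, so that the later samples are kept. Report the number of sites as a descriptive or quality measure, together with input amount and instrument.

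This changes endpoint wording and analysis code. Cellular expression profiling, phospho-proteomics and the software are already in Section 11, so no new samples are needed.

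There are real costs. Intensities have missing values where a count has none, and under the rule in Section 17, sites with more than 20% missing within a group would be descriptive only. The same should apply to sites without a quantified parent protein. Normalisation reduces the effect of low input but does not remove it.

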9.1 STUDY POPULATION (incident patients)

Inclusion criteria

1. Clinical diagnosis of idiopathic nephrotic syndrome (nephrotic range proteinuria uPr/uCr ratio > 2mg/mg, hypoalbuminemia < 3.0 g/dl, oedema);
2. No previous treatment for INS
3. age between 1 and 18 years at onset
4. signed informed consensus

Exclusion criteria

1. Congenital or infantile nephrotic syndrome (age < 1 year old); secondary nephrotic syndrome; glomerulonephritis; autoimmune diseases; vasculitis.
2. Absence of signed informed consensus
3. previous treatments with prednisone or prednisolone for INS

9.2 CONTROL GROUP

Inclusion criteria

1. Clinical diagnosis of minor congenital abnormalities of kidney and urinary tract
2. Absence of proteinuria (uPr/uCr < 0.2 mg/mg)
3. age below 18 years
4. signed informed consensus

Exclusion criteria

1. Immune-mediated diseases not associated with proteinuria (glomerulonephrities)
2. age > 18 Years

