SC NEFROLOGIA E DIALISI PEDIATRICA – TRAPIANTI DI RENE – Direttore: [name]

[contact]

email: [contact]

that biomarkers obtained from liquid biopsies (blood and urine) will improve the stratification and prognosis of INS patients, allowing for accurate tailoring of treatments. As the pathogenesis of the disease is multifactorial, an integrated cellular and secretome multi-omics approach will allow for the identification of biomarkers across multiple levels, to be then validated in the routine clinical setting.

7. Objectives

The **PRIMARY OBJECTIVE** of the **PRECISE** study is the generation of a predictive model to differentiate children with SRNS or SDNS from patients with IRNS at the onset through the integration of -omics, genetic, and clinical data (biomarker signature).

The following **4 SECONDARY OBJECTIVES** will be pursued in the study:

1. Definition of the genetic/epigenetic modifications participating in the pathogenesis of INS.
2. Evaluation of adaptive immune system alterations in INS children.
3. Identification of specific protein patterns in serum and urine in different INS subtypes.
4. Description of the molecular characteristics in healthy children.

8. Methods

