8.1 Study design

Open, multicenter, non-pharmacological observational study.

[figure not shown]
Dipartimento Area Materno - Infatile

SC NEFROLOGIA E DIALISI PEDIATRICA – TRAPIANTI DI RENE – Direttore: [name]

[contact]

email: [contact]

Pediatric Idiopathic nephrotic syndrome

The PRECISE study is an open, multicenter, non-pharmacological biological study. The study will recruit a total of 310 INS patients and 40 controls. In details, the study will recruit 110 treatment-naïve childhood INS patients as a discover cohort, who will be followed for 12 months. At enrolment urine and blood samples will be collected as for normal clinical practice for the planned analysis. At the 12-month follow-up, patients will be classified according to international guidelines as steroid-dependent (SDNS)/frequent relapsing (FRNS) and infrequent relapsing nephrotic

Dipartimento Area Materno - Infatile

SC NEFROLOGIA E DIALISI PEDIATRICA – TRAPIANTI DI RENE – Direttore: [name]

[contact]

email: [contact]

syndrome (IRNS) (10). Additional assessments and biological samples will be performed according to the study flowchart and as described in the study procedure chapter. A homogeneous control group (n=40) by age of children undergoing sampling for minor urological surgical correction procedures will be also enrolled. In the validation phase, biological samples from an independent group of prevalent INS (200 cases) cases will be collected.

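### The 40 controls are called healthy, but entry requires a congenital kidney or urinary-tract abnormality, so secondary objective 4 cannot be met as worded

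*Protocol*

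**What the plan says.** Section 9.2 sets the entry rules for controls. Inclusion criterion 1 is "Clinical diagnosis of minor congenital abnormalities of kidney and urinary tract". The other rules require a urine protein/creatinine ratio below 0.2 mg/mg, an age below 18 years and signed consent, and they exclude certain immune-mediated diseases.

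Section 8.1 describes the same group by its source, without calling it healthy: "A homogeneous control group (n=40) by age of children undergoing sampling for minor urological surgical correction procedures will be also enrolled".

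Section 13 combines both descriptions: "A homogeneous age control group of healthy children undergoing minor urological surgical corrections".

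Secondary objective 4 in Section 7 reads "Description of the molecular characteristics in healthy children". Endpoint 9 in Section 8.3 serves that objective: "To describe different molecular signatures (characteristics) for healthy children group". Endpoints 3, 4, 6, 7 and 8 in the same section also name healthy children as the group against which the INS subtypes are compared.

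**The concern.** A child without a kidney or urinary-tract abnormality cannot enter the control group, yet the protocol assigns that group the task of representing healthy children. Objective 4 has no other purpose than to characterise healthy children, so its target population and its enrolled population do not match.

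The point matters most for urine. Endpoint 6 (concentration and size of urine extracellular vesicles, EVs) and the urine part of endpoint 7 (EV surface proteome) use material from the organ system in which criterion 1 requires an abnormality. A reader who sees an INS-versus-healthy difference there would take it as the effect of INS against normal physiology. A molecular profile reported under objective 4 could likewise be reused as a normal paediatric reference.

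**Working it through.** No figure in the protocol can be recomputed here: the 40 controls are a feasibility number with no calculation behind it. The check sets the sections side by side.

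1. **Who can be a control?** Under Section 9.2, only a child with the diagnosis in criterion 1. The share of controls with it is 40/40 = 100% by design, and 0 of 40 can be free of it.

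2. **Is there another group that could supply healthy data?** No. Section 8.1 enrols 310 INS patients (110 incident plus 200 prevalent) and 40 controls. The healthy children in Sections 7, 8.3 and 13 must be these 40.

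3. **Which statements carry the label?**

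| Item | Calls the group healthy? | Material |
|---|---|---|
| Objective 4 and endpoint 9 | yes, and describe only this group | all types |
| Endpoints 3 and 4 | yes, as comparator | blood cells |
| Endpoint 5 | no control group named | B and T cells |
| Endpoint 6 | yes, as comparator | urine |
| Endpoint 7 | yes, as comparator | urine and serum |
| Endpoint 8 | yes, as comparator | serum |
| Primary objective and endpoint | controls not used | – |

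That is one of four secondary objectives and six of nine secondary endpoints.

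4. **Do the other entry rules restore the label?** They support a comparator without proteinuria and without the excluded immune-mediated diseases. They do not remove the abnormality. Criterion 1 names the kidney as well as the urinary tract, does not define minor, and does not make the surgery mentioned in Sections 8.1 and 13 a condition of entry.

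5. **Is it acknowledged or handled elsewhere?** The limitations in Section 17 do not mention it. That section promises adjustment for confounders where possible, but with no unaffected control there is no information within the control group from which to estimate the effect of the abnormality.

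6. **Could it be examined later?** Perhaps not. Schedules A and C in Section 1 have a medical-history row and schedule B (controls) has none. Section 10.4 asks for medical history at enrolment in general terms, but the control schedule does not carry that through, so anomaly type and site may go unrecorded.

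**The case against.** The best reply is that the protocol is open about where its controls come from. Section 13 puts the health label and the urological surgery in one phrase, which suggests a working meaning of healthy: no nephrotic and no immune disease. The protein threshold and the exclusion criterion fit that meaning, and the abnormalities are described as minor. The study calls itself descriptive, explorative and a pilot. On this view the fault is one of terminology.

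Much of this stands. The source of the controls is disclosed, and the group is usable as a non-proteinuric comparator. But the working meaning is nowhere stated, and objective 4 and endpoint 9 use the word without qualification, as the population to be described. For those two items the word is the whole content.

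It is also fair to object that bias in the urine measures is not demonstrated. A reader might infer that urine differences between INS and controls are known to mix two conditions. The protocol does not support that: it gives neither size nor direction for any shift, and the 100% above counts children with a diagnosis, not an effect on results. Plausibility rests on anatomy alone, and for the blood and serum measures the link is less direct still.

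A reader might further suppose that dropping children with kidney or upper-tract anomalies would yield a healthy reference. It would not, because every remaining child still meets criterion 1.

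**Conclusion.** The contradiction is in the current text and should be resolved. As worded, objective 4 and endpoint 9 cannot be answered with the children enrolled. The control contrasts in endpoint 6 and the urine part of endpoint 7 support a statement about INS against non-proteinuric children with minor urological abnormalities, not about INS against health. Endpoints 3, 4 and 8 and the serum part of endpoint 7 share the label problem.

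The size is all 40 controls by design. The effect on any measured quantity is possible but cannot be quantified from the protocol.

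Three stronger readings do not follow. The controls are not unusable and need not be replaced. Endpoint 5 is not affected through this label, since it names no healthy group. The primary comparison of SRNS/SDNS with IRNS, and the within-INS contrasts in the secondary endpoints, do not depend on the controls.

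The verdict assumes that criterion 1 is applied as written. If it was meant only to describe the surgical source of the children, Section 9.2 itself needs to be reconciled with the word healthy.

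**What to change.** - Reconcile Sections 7, 8.3, 9.2 and 13 by using one name for the group, such as non-proteinuric controls with minor urological abnormalities.
- Restate objective 4 and endpoints 3, 4, 6, 7, 8 and 9 with that name.
- Add to Section 17 that the controls are not a healthy population sample and that urine contrasts with INS should be read accordingly.
- Record anomaly type and site for each control in the eCRF, and add the item to schedule B. This is easiest while data collection is running.
- Describe the urine EV results by anomaly site as an exploratory check only. With 40 controls the subgroups may be small, and none of them gives a healthy reference.

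Recruitment, sampling and the primary analysis do not change. The cost is wording, one extra data item and one descriptive table. The drawback is a less general claim for objective 4.
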